For ambulatory individuals with iSCI, **residual balance deficits negatively impact three major areas of concern during walking: stability, speed, and endurance.** To walk, one must be able to balance [8-10], which is encompassed by the ability to control one's center of mass (COM) dynamics as the body progresses over a continuously changing base of support [11]. Following iSCI, sensory and motor deficits impair balance [12, 13], directly impacting walking function [14, 15]. Individuals with iSCI compensate for balance impairments by selecting gait patterns that passively assist in recovery from movement errors [16]. *Passive* infers that the body will "self-correct" when errors occur without requiring a sensory-motor response, making this method of balance desirable for people with iSCI. These passive mechanisms include decreasing walking speed [17] and step length [18], as well as increasing step width [18-21] and double support time [16, 22]. There are trade-offs associated with choosing gait kinematics that rely on passive mechanisms to provide dynamic balance. Increasing double-support time creates a more stable base of support but limits maximum walking speed [8, 23]. Similarly, taking wider steps creates a larger base of support but makes it more difficult to change directions [24] and significantly increases metabolic energy consumption [19]. In individuals with iSCI, 10% of the total metabolic energy required to walk is expended to maintain lateral balance [21]. These balance deficits contribute to high fall rates [25] (~75% of individuals with iSCI fall each year [25] and most falls occur during walking [26]) and the avoidance of walking in challenging environments [27]. Thus, **interventions that can effectively enhance dynamic balance should enable individuals to select faster, more metabolically efficient gait patterns, without compromising safety.**

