Quantification of walking in the movement amplification environment was initially assessed in non-impaired participants where the effects of the environment could be isolated from neuromuscular impairment. Fifteen healthy participants walked for 10 minutes at their preferred speed in the movement amplification environment, with the gain set to 55 Nsm^{-1} , the peak gain that will be used in the proposed intervention. Participants adapted their steady-state walking patterns in response to the challenge of controlling their lateral COM motion in the movement amplification environment (Figure 4). Following 10 minutes of walking in the movement amplification environment, people adapted their gait patterns to reduce their peak lateral COM speed each stride (14% slower than baseline walking). However, this metric was 73% more variable in the movement amplification environment than during normal walking. Controlling lateral motion required energy. Metabolic cost of transport was 18% larger in the movement amplification environment than during baseline walking. Control was achieved by regulating foot placement each step. Lateral foot placement was significantly more correlated to COM dynamics ($p < 0.05$); regression R^2 was 0.82 in the movement amplification environment compared to 0.71 during baseline walking. When walking in the movement amplification environment **individuals selected gait patterns that stressed active control of lateral motion**. In addition, the increased step-to-step variability of COM speeds may facilitate exploration of movement dynamics that may be beneficial for motor learning [54]. These findings suggest that gait training in a movement amplification environment may be valuable for training impaired populations to actively control dynamic balance during walking.

Lane Width Optimization Test: A Method to Assess Dynamic Balance during Walking

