Finally, we will measure the intervention's potential impact on quality of life. We will utilize an abbreviated version of **The World Health Organization Quality of Life scale (WHOQOL-BREF)** [93]. The WHOQOL-BREF is a 26-item self-report quality of life assessment focusing on areas such as physical, psychological, social and environmental health. Two of the three participants in our case series investigating the effect of locomotor training performed in a movement amplification environment reported substantial improvements in bowel/bladder and sexual function following training. This is consistent with a previous locomotor training study [94] that also found improvements in bladder function. These improvements may be attributable to neuroplasticity or biomechanical demands related to pelvic floor and core musculature involvement in dynamic balance during locomotion. We will use the **International Consultation on Incontinence Questionnaire-Urinary Incontinence Short Form (ICIQ- UI SF)** a 4-item self-report of urinary incontinence to document changes in bladder function [95].

Laboratory Assessments

We will perform laboratory assessments to make quantitative measures of changes in dynamic balance during walking. Specifically, we will quantify the ability of participants to control their whole-body COM motion during treadmill walking and measure associated stepping mechanics. We will collect kinematic data as participants perform walking on an oversized treadmill (Tuff Tread, Willis, TX). We will record 3D coordinates of 40 reflective markers placed on the trunk, pelvis and lower limbs using a 12-camera motion capture system (Qualisys, Gothenburg Sweden). The participant will not be allowed to use any assistive devices (canes, walkers, handrails, or manual assistance) with the exception of any passive ankle-foot orthoses they would typically wear during community ambulation. All walking will be performed at the participant's preferred treadmill speed (identified at the beginning of each Laboratory Assessment testing session through a staircase method of increasing and decreasing the treadmill speed until desired speed is confirmed through verbal feedback). For the Mid, Post, and Follow Up assessments, walking will be performed at both the current preferred treadmill speed (if preferred treadmill speed has changed with training) and at the preferred treadmill speed identified during BSL.

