Participants will perform a series of 2-minute long walking trials performed at both their current preferred walking speed and matched to their preferred walking speeded identified during BSL. Two walking trials at each speed will be used to identify participant's preferred walking characteristics. During these trials, participants will be instructed to walk as they feel most comfortable. No additional external support or feedback will be provided during these trials. Two additional walking trials at each speed will be used to assess the ability of the participant to control

their lateral COM motion during walking. During these walking trials, participants will perform the **Lane Width Optimization Test**. The order of all trials will be randomized. Participants will rest for at least 2 minutes between trials. Additional rest time will be provided as need.

We will post-process and analyze data from the walking trials to assess COM motion and stepping characteristics. Kinematic marker data will be processed using Visual3D (C-Motion, Germantown, MD) and a custom MATLAB (Mathworks, Natick, MA) program. Marker data will be gap-filled and low-pass filtered (Butterworth, 6 Hz cut-off frequency). Time of initial foot contact (IC) and toe-off (TO) events will be identified for each step based on fore-aft positions of the calcaneus and 2nd metatarsal markers. Medio-lateral COM position will be calculated in Visual3D as the center of the Visual3D model's pelvis. To characterize medio-lateral control of the COM during all walking trials we will identify **peak lateral COM Speed** and **lateral COM Excursion** each stride. COM velocity will be calculated as the derivative of COM position. Peak lateral COM Speed will be identified as the maximum absolute COM velocity between ipsilateral initial contact events, and lateral COM Excursion will be calculated as the difference between the maximum and minimum lateral COM positions per stride. To assess how control was instituted, we will examine **step width**, **step length**, **step time**, and **minimum lateral margin of stability** (MOS) each step using established methods [82].

Daily Stepping

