Specific Aim 1: To test if our primary measure, changes in dynamic balance during walking, is different between the two groups following the two interventions, we will compare changes in participants' COM lateral excursion during the lane width optimization test across the four assessment periods (BSL, Mid, Post, Follow Up) and between intervention groups (Control and Experimental). To account for the correlation that arises from measuring multiple data points within each participant over time (i.e. data measured from the mid- assessment period from a specific participant will bear more resemblance to data measured from the BSL- assessment period from the same participant than a different participant) we propose to model the primary outcome using a linear mixed effects model. We will use an indicator variable for the group assignment, i.e. 1=Experimental, 0=Control, to test for the effect of intervention while controlling for potential confounders such as initial walking speed, severity and location of the SCI, spasticity, and age. The strength of the linear mixed effects models is that it can accommodate multiple data points from a single participant and can also handle missing data when data is missing at random. We will apply a similar strategy for fitting a secondary analysis to examine changes in preferred walking characteristics (average and variability of step width, step length, and minimum lateral MOS) and outcome measures (10 MWT, FGA, ABC etc.) across the four assessment periods and between intervention groups. We will transform the variables, such as log-transformation, as needed to meet the model assumption of normality.

Specific Aim 2: To test if our primary measure, changes in steps per day, are different following the two interventions, we will compare changes in participants' average steps per day across the three assessment periods (BSL, Post, Follow Up) and between intervention groups (Control and Experimental). Similar to the methods proposed above, we will model the primary outcome using a linear mixed effects model. We will use an indicator variable for the group assignment, i.e. 1=intervention, 0=control, to test for the effect of intervention while again controlling for potential confounders such as initial walking speed, severity and location of spinal cord injury, spasticity, and age.

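### Must the Aim 1 analysis name the treadmill speed and the Lane Width trials that supply the primary excursion value?

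*Combined protocol and SAP*

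**What the plan says.** **Test conditions.** Section 5.1 (Laboratory Assessments) has preferred treadmill speed "identified at the beginning of each Laboratory Assessment testing session through a staircase method". At Mid, Post and Follow Up, "walking will be performed at both the current preferred treadmill speed (if preferred treadmill speed has changed with training" and also at the preferred speed found at BSL. On trials it says "Two additional walking trials at each speed will be used to assess the ability of the participant to control" lateral COM motion, and these are the Lane Width trials.

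**Outcome.** Section 5.6 (Specific Aim 1) compares changes in "COM lateral excursion during the lane width optimization test across the four assessment periods" between the arms with a linear mixed effects model, "controlling for potential confounders such as initial walking speed, severity and location of the SCI, spasticity, and age". The sample-size text in 5.6 takes the excursion at the narrowest lane achieved and speaks of a reduction in its minimum. The test description in section 2.0 lists both the narrowest lane and the excursion over 5 consecutive gait cycles as primary measures.

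**Speed in the test description.** Section 2.0 describes a two-minute walk at preferred speed, and the 12 pilot participants with iSCI were tested that way.

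**The concern.** From Mid onward a participant whose preferred speed has changed has two sets of Lane Width trials, and nothing says which set is the outcome. The current speed is chosen after randomisation and could respond to training.

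The documents give reasons for movement in either direction. Section 2.0 argues that interventions which "enhance dynamic balance should enable individuals to select faster, more metabolically efficient gait patterns". If the Experimental arm gains more balance, it may therefore also gain more speed. Against that, "Metabolic cost of transport was 18% larger in the movement amplification environment than during baseline walking" (in non-impaired participants), and training speed is governed by heart rate and perceived exertion, so the Experimental arm might train more slowly.

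If current-speed trials were used, or all trials were pooled, a between-arm difference in speed change could enter the balance comparison. Initial walking speed, the only speed among the named covariates, would not remove it. Three further worries follow:

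- Participants whose speed changed would contribute four values per visit against two for the others.
- A best-of-session rule would compare two attempts at BSL with up to four later.
- An analyst could pick the speed that gives the better result.

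**Working it through.** **The plan's own figure.** The plan gives no number on this point. The nearest is 7 per group in 5.6. Reading the 20% difference as 0.20 × 0.083 m = 0.0166 m, with SD 0.014 m, two-sided 5% and 80% power, the usual two-sample formula gives 2 × (1.96 + 0.842)² × 0.014² / 0.0166² = 11.2, so 12 per group. That mismatch is a separate matter. Below, 0.0166 m serves only as a yardstick.

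**Trial counts.** BSL: 2. Each later visit: 2 if speed is unchanged, 4 if changed. Minimum 2 + 3 × 2 = 8; maximum 2 + 3 × 4 = 14. At BSL the two candidate definitions coincide, and for anyone whose preferred speed stays the same they coincide throughout.

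**Choosing the speed after seeing results.** With two candidate test statistics correlated at r, the chance that at least one is significant under no effect is 1 − P(|Z₁| < 1.96, |Z₂| < 1.96), bivariate normal. The correlations are assumptions.

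| r | false-positive rate |
|---|---|
| 0.5 | 9.07% |
| 0.7 | 8.35% |
| 0.8 | 7.81% |
| 0.9 | 7.04% |
| 0.95 | 6.46% |
| 0.98 | 5.93% |
| 0.99 | 5.7% |
| 0.995 | 5.5% |

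The shared BSL value and the identical data from participants with unchanged speed make the high end more plausible. Allowing the average of the two speeds as a third option gives 9.6%, 8.6%, 7.9%, 7.2% and 6.5% at r = 0.5, 0.7, 0.8, 0.9 and 0.95. With the speed fixed beforehand the rate is 5%, whichever speed is fixed.

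**Best-of-session reading.** For exchangeable normal trials the expected minimum is −0.564 trial SD for two attempts and −1.029 for four, a drop of 0.465 SD with no true change. With an assumed within-person trial SD of 0.003 to 0.007 m this is 0.0014 to 0.0033 m, or 8% to 20% of 0.0166 m. It applies only to participants whose speed changed. The shift in the arm contrast is this amount times the between-arm difference in the proportion who changed. It is zero if the proportions are equal, and reaches the full amount only if everyone changes in one arm and no one in the other.

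**Speed difference between arms.** The contrast at current speed differs from the contrast at BSL speed by (excursion change per m/s) × (between-arm difference in speed gain). The documents give neither factor. Assuming 0.02 to 0.06 m per m/s and 0.05 to 0.20 m/s, the result runs from 0.02 × 0.05 = 0.001 m to 0.06 × 0.20 = 0.012 m, or 6% to 72% of 0.0166 m. Such a wide range from assumed inputs shows that the two contrasts can differ. It does not show that either is wrong.

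**The case for a change.** The strongest case for a change is that this is the primary test of Aim 1, that the text does not fix its outcome variable, and that one sentence would close the gap without new data. The preferred-speed wording in section 2.0 does not settle the matter, because 5.1 then adds a second speed. The mixed model does not choose an estimand, and randomisation does not equalise a speed chosen afterwards. All of this stands as a description of the text.

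It does not carry as far as a required change. Both arms are tested under the same rule. Excursion at current preferred speed compares balance as participants now choose to walk; excursion at BSL speed compares balance with speed held constant. Both are legitimate randomised comparisons. BSL speed keeps trial numbers equal, but it departs from the preferred-speed condition in which the pilot work showed convergent validity. Requiring a mean of two trials would also sit uneasily with the narrowest-lane and minimum wording in 5.6.

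Unequal trial numbers do not in themselves bias a mixed model, and the covariate list is introduced with examples, so it is not closed. The best-of-session rule is only one possible reading; no section states it.

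A further worry is that BSL-speed trials may be left uncompleted by people who have worsened, while 5.6 relies on a model that "can also handle missing data when data is missing at random". That is a missing-data question, separate from which speed is primary. The documents do not say why a trial might be uncompleted, and fatigue or a technical fault are other possible reasons.

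**Conclusion.** The omission is genuine, but it is missing detail that analysts can fill sensibly. A team that deliberately repeats the test at BSL speed has the data for a speed-constant comparison and for one at preferred speed, with excursion as the variable in both analysis passages of 5.6. Choosing between the speeds is a fair trade-off, and the documents show no wrong result under either.

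The only general cost is conditional. If the speed were selected after seeing results, the 5% error rate would rise to 5.9% to 7.0% at assumed correlations of 0.98 to 0.9, and to 9.1% at 0.5. Nothing in the documents indicates such selection. Any bias from differential speed change cannot be sized or signed, because the documents give no relation between speed and excursion and point in both directions on which arm would speed up more.

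This rests on the text supplied. Part of the pilot description was not available, and the manual of study procedures listed in the 5.1 timeline is not among the documents. No change to the plan follows.

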5.2 Recruitment Methods

- **State how many subjects will be needed.**

We will enroll 46 participants with iSCI in the study.

- **Describe when, where, how and by whom potential subjects will be identified and recruited.**

We will enroll 46 participants with iSCI in the study. Veterans will be recruited from the Spinal Cord Injury Service at Edward Hines Jr. VA Hospital. During the last three years the Hines Spinal Cord Injury Service treated 553 unique patients with SCI. We will work with a highly experienced clinical coordinator at the Edward Hines Jr. VA Hospital to recruit participants from this facility. [name] has established a strong professional relationship with the clinical staff from the Spinal Cord Injury Service to identify, contact, and screen potential study participants. [name] has been involved with multiple SCI related studies in the past, including studies run by the PI of the proposed study. Her familiarity working with the target study population and their clinical providers will be an asset to the proposal. We anticipate that the pool of eligible participants available through the Edward Hines Jr. VA Hospital may not be sufficient to meet our full enrollment objective.

As needed, additional Veteran and non-Veteran participants will be recruited through the Shirley Ryan AbilityLab. The Shirley Ryan AbilityLab maintains the *Clinical Neuroscience Research Registry* a database of interested, potential study volunteers with SCI. The Registry is populated through referrals from associated inpatient and outpatient physical therapy clinics of the Shirley Ryan AbilityLab and through postings at clinics, support groups, and SCI organizations. The volunteer database currently has 475 volunteers with up-to-date-contact information. Of these volunteers greater than 215 individuals identify that they are able to walk in therapy, home or the community. Individuals registered in the database have consented to allowing researchers to contact them directly to discuss opportunities to participate in ongoing research projects. [name], a co-Investigator on this proposal, jointly oversees the maintenance and population of the volunteer database. She will ensure that the study team receives access to the database. In addition, the Shirley Ryan AbilityLab treats ~140 SCI inpatients and 225 SCI

outpatients a year. Collectively, the potential pool of study participants available between the Edward Hines Jr. VA Hospital and the Shirley Ryan AbilityLab will be more than adequate to meet the requirements for the proposed trial.

- **Describe materials that will be used to recruit subjects, e.g., advertisements. Include materials as an appendix or separate attachment.**

We will employ a multi-faceted approach to recruiting and enrolling 46 individuals with iSCI needed for this study.

First we will recruit veterans with spinal cord injury from the Spinal Cord Injury Service at Edward Hines Jr. VA Hospital. We will recruit individuals using the following means.

- [name] will contact clinical staff from the Spinal Cord Injury service. These individuals will be provided with a recruitment flyer attached. Clinical staff will be asked to post and/or provide the recruitment flyer to potential participants. The fly directs potential participants to contact the study PI and research staff by phone or mail.
- Recruitment flyers will be posted in the Spinal Cord Injury Service at the Edward Hines Jr. VA Hospital. Interested individuals will be directed to contact the study PI and research staff by phone or mail.

Second, additional veteran and non-veteran subjects with incomplete spinal cord injury will be recruited through the *Clinical Neuroscience Research Registry*, a database of interested, potential study volunteers with SCI, which is maintained by the Shirley Ryan AbilityLab

- Individuals registered in the database have consented to allowing researchers to contact them directly to discuss opportunities to participate in ongoing research projects. [name] and approved study personal will call qualified individuals from the database to discuss participation in the study.
- Recruitment flyers will be posted in the lobby of the Shirley Ryan AbilityLab and on SCI outpatient floors. Interested individuals will be directed to contact the study PI and research staff by phone or mail.

Third, the PI will reach out to the Paralyzed Veterans of America local chapter and the Illinois Spinal Cord Injury Association. The PI will request to present the study in person at upcoming meetings and will ask if the study flyer can be distributed to members either through the organization's print or web-based newsletter. Interested individuals will be directed to contact the study PI and research staff by phone or mail.

Fourth, study information will be posted on <http://www.clinicaltrials.gov>. Interested individuals will be directed to contact the study PI and research staff by phone or mail.

Finally, a recruitment will be posted on the PI's laboratory website. Interested individuals will be directed to contact the study PI and research staff by phone or mail.

- **Describe any payments to subjects, including the amount, timing (at the end of the study or pro-rated for partial study participation), method (e.g., cash, check, gift card), and whether subjects will experience a delay in receiving the payment.**

All participants will receive a stipend of \$25 for visits including laboratory assessments and clinical outcome measures or \$20 for visits that include participation in the locomotor training intervention. Participants will also receive vouchers for parking.

